
[figure not shown]
Apple Watch SE

Apple Watch Series 4 and Apple Watch Series 5

Apple Watch Series 3

WARNING: For important safety information about the battery and charging Apple Watch, see [Important safety information for Apple Watch](#).

Check remaining power

To see remaining power, touch and hold the bottom of the screen, then swipe up to open Control Center. To more quickly check the remaining power, add a battery complication to the watch face. See [Customize the watch face](#).

Save power when the battery is low

You can put your Apple Watch in Power Reserve mode to stretch the remaining battery power. Your Apple Watch still displays the time, but you can't use apps.

1. Touch and hold the bottom of the screen, then swipe up to open Control Center.
2. Tap the battery percentage, then drag the Power Reserve slider to the right.

Tip: If you have battery-powered devices such as AirPods connected to your Apple Watch through Bluetooth, their remaining charge appears on this screen.

When battery charge drops to 10 percent or lower, your Apple Watch alerts you and gives you the opportunity to enter Power Reserve mode.

When your Apple Watch is almost out of power, it enters Power Reserve mode automatically.

Tip: For tips on maximizing battery life, see [Maximizing Battery Life and Lifespan](#) at the Apple website.

Return to normal power mode

Restart your Apple Watch—press and hold the side button until the Apple logo appears.

The battery must have at least 10 percent charge for your Apple Watch to restart.

Check time since the last charge

1. Open the Settings app  on your Apple Watch.
2. Tap Battery.

The Battery screen shows the remaining battery percentage, a graph that details the recent history of the battery charge, and information about when the battery was last charged.

You can also check the time since last charge on iPhone. Open the Apple Watch app on iPhone, tap My Watch, then go to General > Usage.

Check battery health

You can find out the capacity of your Apple Watch battery relative to when it was new.

1. Open the Settings app  on your Apple Watch.

2. Tap Battery, then tap Battery Health.

To reduce battery aging, Apple Watch learns from your daily charging routines so it can wait to finish charging past 80 percent until you need to use it.

Apple Watch alerts you if battery capacity is significantly reduced, allowing you to check your service options.

Track important health information with Apple Watch

Your Apple Watch can help you meet your sleep goals, track important information related to your heart, check your blood oxygen levels, and encourage you to wash your hands.

Prioritize your sleep

Apple Watch can help you create a sleep schedule, track your sleep, then report your sleep trends over time. To get started, open the Health app on iPhone and create a sleep schedule. Then wear your watch to bed and Apple Watch does the rest.

Get heart health notifications

You can enable notifications from the Heart Rate app on your Apple Watch to alert you to high or low heart rates. The irregular heart rhythm notification on the Apple Watch can also alert you if an irregular rhythm suggestive of Atrial fibrillation is identified. Open the Apple Watch app on your iPhone, go to My Watch, then tap Heart. Turn on High Heart Rate or Low Heart Rate, then set a heart rate threshold, also turn on irregular rhythm notifications.

Check your blood oxygen levels (Apple Watch Series 6 only)

Use the Blood Oxygen app  to measure your blood oxygen levels directly from your wrist. See the most recent measurement on your Apple Watch and a record of all your readings in the Health app on iPhone.

Wash your hands thoroughly

Turn on Handwashing in the Apple Watch app on iPhone, and your Apple Watch encourages you to keep going for 20 seconds, the time recommended by global health organizations. Your watch can also notify you if you haven't washed your hands within a few minutes of returning home.

Track your menstrual cycle

Use the Cycle Tracking app  to log daily information about your menstrual cycle. The app uses that information to provide period and fertility window predictions.

APPENDIX B: SYNC COMPONENTS

Study participants randomized to the Intervention Arm will use a version of SYNC that makes behavioral recommendations to correct circadian misalignment. Those in the Control Arm will use a “dummy” version of the app that makes behavioral recommendations that should minimally affect the circadian clock.

The full version of SYNC has the following features:

- Light exposure recommendations; e.g. times to sit near a window or go outside
- Light avoidance recommendations; e.g. times to wear blue-blocking glasses
- Caffeine avoidance recommendations
- Ideal times to sleep
- Ideal times to exercise for peak performance
- Ideal times to exercise to shift the circadian clock
- Surveys embedded for daily tracking of fatigue and other metrics
- Personalized educational information about the circadian clock

The dummy version of SYNC has the following features:

- Light exposure recommendations, timed to avoid shifting circadian rhythms
- Surveys embedded for daily tracking of fatigue and other metrics

The abovementioned recommendations are calculated using mathematical models of the circadian clock which read in data from the user’s wearable device. The times are expected to shift every day, as the user’s circadian clock shifts.

Sample behavioral recommendations from the full app include:

- *“Sit near a window or go outside from 8:30 am - 9:45 am”*
- *“Put on your blue-blocking glasses at 7:05 pm”*
- *“To fall asleep earlier tonight, do a workout between 6:45 am and 9:30 am”*
- *“Your peak window of athletic performance is from 7:45 pm - 9:45 pm”*
- *“Taking a nap from 1:00 - 1:45 pm today shouldn’t keep you from falling asleep tonight.”*

The dummy version of the app will make the following recommendations:

- *“Put on your study-provided glasses from 12:00 pm - 1:00 pm”*
- *“Be in a room with normal lighting from 1:00 pm - 1:30 pm”*

A screenshot of the app, currently in revision, is provided below for context:

9:41 

Task points: **Halfway there!**

 Progress Goal

Circadian state: In sync

 Learn more about how staying in sync helps you sleep! 

Daily Tasks

 **Blue blocking glasses**
from 8p - 11p 
Incomplete 1 point for completion

 **Lights out**
from 11p - 6a 
Incomplete 5 points for completion

Completed tasks

 **Bright white light**
from 9a - 10a 
5 points for completion

 **Moderate light**
from 10a - 3p 
1 point for completion

APPENDIX C: USER-REPORTED OUTCOME MEASURES

Baseline Survey/Exit Survey

PROMIS® Item Bank v1.0 – Sleep Disturbance – Short Form 8a

Sleep Disturbance – Short Form 8a

Please respond to each question or statement by marking one box per row.

In the past 7 days...		Very poor	Poor	Fair	Good	Very good
Sleep109	My sleep quality was	 5	 4	 3	 2	 1
In the past 7 days...		Not at all	A little bit	Somewhat	Quite a bit	Very much
Sleep116	My sleep was refreshing.	 5	 4	 3	 2	 1
Sleep20	I had a problem with my sleep	 1	 2	 3	 4	 5
Sleep44	I had difficulty falling asleep	 1	 2	 3	 4	 5
Sleep108	My sleep was restless	 1	 2	 3	 4	 5
Sleep72	I tried hard to get to sleep	 1	 2	 3	 4	 5
Sleep67	I worried about not being able to fall asleep	 1	 2	 3	 4	 5
Sleep115	I was satisfied with my sleep.	 5	 4	 3	 2	 1

Emotional Distress - Anxiety – Short Form 7a

Please respond to each item by marking one box per row.

In the past 7 days...

		Never	Rarely	Sometimes	Often	Always
EDANX01	I felt fearful.....	 1	 2	 3	 4	 5
EDANX05	I felt anxious.....	 1	 2	 3	 4	 5
EDANX30	I felt worried.....	 1	 2	 3	 4	 5
EDANX40	I found it hard to focus on anything other than my anxiety.....	 1	 2	 3	 4	 5
EDANX46	I felt nervous.....	 1	 2	 3	 4	 5
EDANX53	I felt uneasy	 1	 2	 3	 4	 5
EDANX54	I felt tense	 1	 2	 3	 4	 5

Emotional Distress – Depression – Short Form 8a

Please respond to each question or statement by marking one box per row.

In the past 7 days...		Never	Rarely	Sometimes	Often	Always
EDDEP04	I felt worthless	 1	 2	 3	 4	 5
EDDEP06	I felt helpless.....	 1	 2	 3	 4	 5
EDDEP29	I felt depressed.....	 1	 2	 3	 4	 5
EDDEP41	I felt hopeless.....	 1	 2	 3	 4	 5
EDDEP22	I felt like a failure	 1	 2	 3	 4	 5
EDDEP36	I felt unhappy.....	 1	 2	 3	 4	 5
EDDEP05	I felt that I had nothing to look forward to	 1	 2	 3	 4	 5
EDDEP09	I felt that nothing could cheer me up.....	 1	 2	 3	 4	 5

Physical Function – Short Form 8b

Please respond to each question or statement by marking one box per row.

		Without any difficulty	With a little difficulty	With some difficulty	With much difficulty	Unable to do
PF11	Are you able to do chores such as vacuuming or yard work?	 5	 4	 3	 2	 1
PF21	Are you able to go up and down stairs at a normal pace?	 5	 4	 3	 2	 1
PF31	Are you able to go for a walk of at least 15 minutes?	 5	 4	 3	 2	 1
PF41	Are you able to run errands and shop?	 5	 4	 3	 2	 1
		Not at all	Very little	Somewhat	Quite a lot	Cannot do
PF51	Does your health now limit you in doing two hours of physical labor?	 5	 4	 3	 2	 1
PF61	Does your health now limit you in doing moderate work around the house like vacuuming, sweeping floors or carrying in groceries?	 5	 4	 3	 2	 1
PF71	Does your health now limit you in lifting or carrying groceries?	 5	 4	 3	 2	 1
PF81	Does your health now limit you in doing heavy work around the house like scrubbing floors, or lifting or moving heavy furniture?	 5	 4	 3	 2	 1

PROMIS® Scale v1.2 – Global Health

Global Health

Please respond to each question or statement by marking one box per row.

		Excellent	Very good	Good	Fair	Poor
Global01	In general, would you say your health is:	 5	 4	 3	 2	 1
Global02	In general, would you say your quality of life is:	 5	 4	 3	 2	 1
Global03	In general, how would you rate your physical health?	 5	 4	 3	 2	 1
Global04	In general, how would you rate your mental health, including your mood and your ability to think?	 5	 4	 3	 2	 1
Global05	In general, how would you rate your satisfaction with your social activities and relationships?	 5	 4	 3	 2	 1
Global06	In general, please rate how well you carry out your usual social activities and roles. (This includes activities at home, at work and in your community, and responsibilities as a parent, child, spouse, employee, friend, etc.).....	 5	 4	 3	 2	 1
Global08	To what extent are you able to carry out your everyday physical activities such as walking, climbing stairs, carrying groceries, or moving a chair?	 5	 4	 3	 2	 1

In the past 7 days...

		Never	Rarely	Sometimes	Often	Always						
Global09	How often have you been bothered by emotional problems such as feeling anxious, depressed or irritable?	 5	 4	 3	 2	 1						
Global08	How would you rate your fatigue on average?	 5	 4	 3	 2	 1						
Global07	How would you rate your pain on average?	 0 No pain	 1	 2	 3	 4	 5	 6	 7	 8	 9	 10 Worst pain imaginable

Morningness-Eveningness Questionnaire:

1. One hears about “morning” and “evening” types of people. Which one of these types do you consider yourself to be?
 - a. Definitely a morning type
 - b. More of a morning than evening type
 - c. More of an evening than morning type
 - d. Definitely an evening type
2. Considering only your own “feeling best” rhythms, at what time would you get up if you were entirely free to plan your day?
 - a. 5 am - 6:30 am
 - b. 6:30 am - 7:45 am
 - c. 7:45 am - 9:45 am
 - d. 9:45 am - 11 am
 - e. 11 am - 12 noon
3. During the first half hour after awakening in the morning, how tired do you feel?
 - a. Very tired
 - b. Fairly tired
 - c. Fairly refreshed
 - d. Very refreshed
4. At what time in the evening do you feel tired and in need of sleep?"
 - a. 8 pm - 9 pm
 - b. 9 pm - 10:15 pm
 - c. 10:15 pm - 12:30 am
 - d. 12:30 am - 1:45 am
 - e. 1:45 am - 3 am
5. At what time of the day do you think that you reach your “feeling best” peak?
 - a. 10 pm - 5 am
 - b. 5 am - 8 am
 - c. 8 am - 10 am
 - d. 10 am – 5 pm
 - e. 5 pm – 10 pm

Daily Fatigue Survey

Carrier 5:48 PM

Done **Daily**

How fatigued are you?

Very fatigued
 Somewhat fatigued
 A little bit fatigued
 Not fatigued at all

 Tasks

 Surveys

 Settings

Weekly Survey

PROMIS Fatigue Short Form 4a

PROMIS® Item Bank v1.0 –Fatigue – Short Form 4a

Fatigue – Short Form 4a

Please respond to each question or statement by marking one box per row.

During the past 7 days...		Not at all	A little bit	Somewhat	Quite a bit	Very much
HI7	I feel fatigued	 1	 2	 3	 4	 5
AN3	I have trouble starting things because I am tired.....	 1	 2	 3	 4	 5
In the past 7 days...						
FATEXP41	How run-down did you feel on average? ...	 1	 2	 3	 4	 5
FATEXP40	How fatigued were you on average?	 1	 2	 3	 4	 5

“How is your experience with the app?” questionnaire

Carrier 5:55 PM Done Weekly Carrier 5:55 PM Done Weekly Carrier 5:56 PM Done Weekly

App Experience	App Experience	App Experience
Is there anything you disliked about the app or glasses this week?	Is there anything you liked about the app or glasses this week?	Is there anything else we should know?

Next Next Next

Tasks Surveys Settings Tasks Surveys Settings Tasks Surveys Settings

Sleep aid usage survey

Carrier 5:54 PM Done Weekly

Sleep Aid Usage

If you have used any sleep aids in the past week, select them from the list below:

- Ambien, Ambien CR (zolpidem tartrate)
- Dalmane (flurazepam hydrochloride)
- Halcion (triazolam)
- Lunesta (eszopiclone)
- ProSom (estazolam)
- Restoril (temazepam)
- Silenor (doxepin)
- Sonata (zelplon)

Carrier 5:55 PM Done Weekly

Sleep Aid Usage

- Lunesta (eszopiclone)
- ProSom (estazolam)
- Restoril (temazepam)
- Silenor (doxepin)
- Sonata (zelplon)
- Desyrel (trazodone)
- Belsomra (suvorexant)
- Antihistamines
- Melatonin
- Alcohol
- Other

Carrier 5:55 PM Done Weekly

In the last week...

Approximately how many alcoholic beverages did you consume?

- 0
- 1-2 drinks
- 3-6 drinks
- 7-12 drinks
- >12 drinks

Next

Tasks Surveys Settings Tasks Surveys Settings

Weekly travel questionnaire:

1. Did you travel across time zones this week?"

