1. STUDY DESIGN

- 1.1. *Study Overview.* This study will use a two-arm randomized study design. Participants will be recruited across three cancer types. Each of the participants will be randomized to an active “intervention” arm (using the full SYNC app) or to a control arm (using a “dummy” version of the SYNC app that gives recommendations for light at times that should not significantly affect the circadian clock). The random allocation of participants to the treatment arm or control arm establishes the basis for testing the statistical significance or difference between the groups in the measured outcome (patient fatigue, assessed by a daily 1-question fatigue survey and the PROMIS 4-item Fatigue). Patient age, gender, and other prognostic baseline characteristics that could potentially confound an observed association, including those that are unknown or unmeasured, will be distributed equally, except through chance alone, through random assignment. Thus, this design is well-suited to our goal of assessing the efficacy of a mobile health intervention, SYNC, on participants.
- 1.2. *Primary Hypothesis.* The primary hypothesis is that a mobile-app delivered circadian intervention (SYNC) will reduce patient fatigue.
- 1.3. *Study Objectives*
 - 1.3.1. Primary Objective. To test the difference between the “intervention” (full SYNC app) arm and the control (limited SYNC app) arm in the measured outcome of patient fatigue, assessed by daily 1 question surveys and weekly 4-item PROMIS questionnaires over the course of 12 weeks.
 - 1.3.2. Secondary Objective. To determine the change in sleep disturbances, anxiety, depression, physical functioning, and global health through PROMIS questionnaires, between baseline and the 12-week assessment in both the control and intervention arms, and to look for differences in this change between the two arms.
 - 1.3.3. Exploratory Objectives
 - 1.3.3.1. Change in patient physical activity through physiological data capture using the wearable sensors in the control versus intervention arm.
 - 1.3.3.2. Change in patient health care utilization (e.g., total count of hospital days, readmissions, and ambulatory care clinic visits) in the control versus intervention arm
 - 1.3.3.3. Change in patient sleep aid usage in the control versus intervention arm.
- 1.4. *Participant Eligibility*
 - 1.4.1. Inclusion Criteria

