 - 1.4.1.1. Able to provide informed consent and willing to sign an approved consent form that conforms to federal and institutional guidelines.
 - 1.4.1.2. Comfortable reading and speaking English.
 - 1.4.1.3. Must own an iPhone 6s or later (with iOS 14 or later or willing to update to iOS 14+) and be willing to complete surveys on it, per the protocol. Alternatively, patients without iPhones must be willing to use a loaner iPhone provided by the study team to use during the study and return at the end of the study.
 - 1.4.1.4. ≥ 18 years of age.

- 1.4.1.5. Sleep aid usage will be allowed as long as the patient has been on a stable dose for at least 4 weeks prior to enrollment and agrees to continue the same dose during the study.
- 1.4.1.6. A response of at least 4 on a 10-point scale (with 0 = not fatigued at all and 10 = extremely fatigued) to the question "How fatigued did you feel in the last four weeks?"
- 1.4.1.7. Breast cancer population: Diagnosed with stage 1-3 breast cancer in the last 10 years, without metastatic disease. Chemotherapy or radiation therapy, if indicated, must have been completed at least 3 months prior to enrollment. Concomitant anti-HER2 therapy and/or anti-endocrine therapy is permitted.
- 1.4.1.8. Prostate cancer population: Undergoing androgen deprivation therapy (ADT) for at least three months and are anticipated to remain on ADT for the duration of the trial. Concomitant additional anti-androgen therapy (e.g., enzalutamide) is permitted.
- 1.4.1.9. HSCT population: Participants must be from the University of Michigan Blood and Marrow Transplant Program.

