- 1.5.4. Participants will be allowed to use sleep aids over the course of the trial. There will be no restriction on their usage; however, subjects will be asked to report on a weekly basis what sleep aids they consumed, as well as the number of alcoholic drinks they consumed. This survey will be carried out in the app.
- 1.5.5. Once the trial has begun, study coordinators will track completion of surveys, and in the event of missing data will follow-up with subjects to assess challenges to encourage survey completion. SYNC software will be maintained in collaboration with Arcascope, Inc. After randomization, subjects will complete baseline assessments, as outlined in the metrics Appendix. They will be asked to wear the wearable device day and night for twelve weeks. During this time, the app will deliver ecological momentary assessments of fatigue daily at random times of day and the validated 4-item PROMIS Fatigue questionnaire weekly to both the control and interventional groups. At the end of the twelve-week period, the subjects will remotely complete end-of-trial assessments.
- 1.5.6. Intervention arm (SYNC app): Participants randomized to the intervention arm will be instructed on how to download the app on their mobile phones (iOS) and how to operate the wearable device. The app will record when the user opens the app, as well as when they check off having completed an assigned task; e.g. “getting bright light exposure”. Please see **Appendix A** to view the components of the wearable device. Please see **Appendix B** to view specifications of the mobile app. Any PHI information will be stored on University of Michigan servers in a secure way. Only non-PHI information will be stored and collected via the Sync app. The SYNC will be downloaded onto patient mobile phones and can be used freely throughout the intervention period because it contains no PHI data.
- 1.5.7. Control arm: Participants randomized to the control arm will be instructed on how to download the SYNC app and how to operate the wearable sensor. Their research ID will trigger the “control” recommendations from SYNC, which are chosen to minimize circadian effect. Any PHI information will be stored on University of Michigan servers in a secure way. Only non-PHI information will be stored and collected via the Sync app. The SYNC will be downloaded onto patient mobile phones and can be used freely throughout the intervention period because it contains no PHI data.

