3. STUDY ENDPOINTS

3.1. *Primary Endpoint.* The primary endpoint is **fatigue**, as assessed by a daily fatigue questionnaire and a weekly 4-item PROMIS fatigue questionnaire.

3.2. *Secondary Endpoint.* The secondary endpoints are sleep disturbance, anxiety, depression, physical function and global health, as measured via the following PROMIS validated instruments:

- PROMIS Sleep Disturbance (8-item)
- PROMIS Anxiety (7-item)
- PROMIS Depression (8-item)
- PROMIS Physical Function (8-item)
- PROMIS Global Health (10-item)

3.3. *Exploratory Endpoints.*

3.3.1. Activity data. Patient activity (steps) and sleep will be measured continuously from the start to the end of the trial through wearable sensors.

3.3.2. Health care utilization data. Patient health care utilization data (e.g., total count of hospital days, emergency department visits, readmissions, and ambulatory care clinic visits) will be captured through the electronic health record as well as self-report (i.e., if the patient is readmitted at an outside hospital other than Michigan Medicine).

3.3.3. Sleep aid utilization data will be collected via self-report in the app once a week.

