5. STATISTICAL CONSIDERATIONS

- 5.1. *Study Design.* The clinical trial is a two-arm randomized controlled trial. After completion of the intervention, data analysis will be conducted according to the statistical analysis plan outlined below. Descriptive statistics will be performed prior to conducting the statistical analyses. An intention-to-treat (ITT) analysis of the results will be based on the initial assignment of the randomized participants. With the ITT approach, participants will be analyzed according to the treatment assignment, even if the participant drops out of the study. The ITT approach minimizes biased comparisons among the treatment arms. Missing data will be imputed using the last collected data from the subject prior to dropout.
- 5.2. *Accrual.* It is estimated that 18-months will be necessary to enroll the targeted sample size. Accrual will be reported by race, ethnicity, gender, and age.
- 5.3. *Study Duration.* Survey results and wearable data will be actively collected from participants over the course of 12 weeks. At the conclusion of the 12 weeks, passive collection of wearable data through the app will continue for up to one year for each participant who opts-in to continue using the app. Medical records may be accessed for up to five years after the conclusion of the 12-week collection period.
- 5.4. *Randomization.* Blocked randomization will be used to limit bias and achieve an equal distribution of participants to the intervention and control arms of the study (69 randomized, 69; with 23 from each cancer population in each arm). This approach will recruit participants in small blocks to ensure that half of the participants within each block will be allocated to the treatment and the other half to the control. The size of the blocks will be permuted to limit selection bias, and within each block, the order of patients will be random. The study statistician will create a randomization list before the study begins enrollment using the statistical package R. This list will be used by the study group in assigning patients to the correct study arm.
- 5.5. *Blinding.* Study arm assignments cannot be blinded to the investigators or the rest of the study team because it will be known whether participants have SYNC on their mobile device or not (due to technical purposes).

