5.14.2. Patient health care utilization. The total count of hospital days, ED visits, readmissions, and ambulatory care clinic visits during the trial, with adjustment for follow-up, will be compared between arms using a Poisson regression model, with adjustment for potential mediating or moderating effects of patient characteristics, if needed. The data will be captured at the time of PRO assessments.

5.14.3. Patient sleep aid utilization. The total number of sleep aids being used by the patients, as well as the types, will be collected via weekly surveys over the course of the trial.

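### The weekly sleep-aid survey records which products were used but not nights or dose, so changes within a continuing sleep aid go unseen and objective 1.3.3.3 is measured insensitively

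*Combined protocol and SAP*

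**What the plan says.** - **Objective.** Study Design 1.3.3.3 lists "Change in patient sleep aid usage in the control versus intervention arm".
- **Instrument.** Endpoint 3.3.3 states: "Sleep aid utilization data will be collected via self-report in the app once a week". Appendix C shows the screens. The item reads "If you have used any sleep aids in the past week, select them from the list below" and is followed by named hypnotics, antihistamines, melatonin, alcohol and an open category. The next screen asks "Approximately how many alcoholic beverages did you consume", answered in bands from 0 to more than 12. That is the only amount requested.
- **Timing.** The Time and Events Table runs this survey weekly from the first day, and Section 5.3 sets the active period: "Survey results and wearable data will be actively collected from participants over the course of 12 weeks".
- **Analysis.** Section 5.14.3 says: "The total number of sleep aids being used by the patients, as well as the types, will be collected via weekly surveys". It names no comparison between arms, whereas 5.14.1 and 5.14.2 each do.
- **Rules on use.** Inclusion criterion 1.4.1.5 admits users on a "stable dose for at least 4 weeks prior to enrollment and agrees to continue the same dose during the study". Study Design 1.5.4, on sleep-aid use after enrolment, reads: "There will be no restriction on their usage; however, subjects will be asked to report on a weekly basis what sleep aids they consumed".

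**The concern.** The objective concerns change in use and the eligibility rule is framed by dose, yet the data item is a yes or no per product per week. Someone who goes from a tablet every night to one night a week, or who halves or doubles the dose, can give the same answer throughout.

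Divergence between arms is plausible. Appendix B gives the full app sleep-timing, caffeine and exercise advice that the dummy app lacks. If sleep-aid use shifted in one arm, that would help explain a difference, or a lack of one, in fatigue or PROMIS Sleep Disturbance. A flat result from the tick-list could be read as evidence that co-treatment stayed the same when its frequency or dose had changed. No other planned data source would allow nights or dose to be rebuilt afterwards.

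**Working it through.** **The plan's own figure.** No figure is given for sleep-aid use. The only sample-size figure is for fatigue (Section 5.7). A two-sample t-test for 0.5 SD at two-sided 0.05 and 80% power needs 63.8, so 64 per arm (power 0.801 at 64). Then 64 / 0.93 = 68.8, so 69 per arm and 138 in total. This reproduces and does not depend on the sleep-aid item.

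**What the tick-list can register.**

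| Change during the study | Seen in number or types? |
|---|---|
| Starts or stops a product | Yes |
| Adds or drops a product | Yes |
| Switches product | Yes, through types; the number is unchanged |
| Fewer or more nights of the same product | Only if a whole week passes without use |
| Lower or higher dose of the same product | No |

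**Chance of a tick.** Assume nights are independent and a product is used on k nights a week on average. Then P(tick) = 1 − (1 − k/7)^7.

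- k = 6: 1 − (1/7)^7 ≈ 1.00
- k = 3: 1 − (4/7)^7 = 1 − 0.020 = 0.98
- k = 2: 1 − (5/7)^7 = 1 − 0.095 = 0.905
- k = 1: 1 − (6/7)^7 = 1 − 0.340 = 0.66

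If use is regular, with exactly k nights every week, P(tick) is 1 for any k of at least 1 and the list is less sensitive still. If use is bunched so that some weeks are empty, it is more sensitive.

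**Power on one week's tick.** Assume 30% to 50% of 64 per arm are users, so n = 19 to 32, each with one product. With a two-sided 0.05 test of proportions p1 and p2 (mean p̄, difference d):

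SE0 = √(2p̄(1 − p̄)/n), SE1 = √([p1(1 − p1) + p2(1 − p2)]/n), power = Φ((|d| − 1.96·SE0)/SE1).

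- *All users in one arm go from 6 nights to 3; the other arm stays at 6.* d ≈ 0.020. For n = 19, SE0 = 0.0322 and SE1 = 0.0320, so power = Φ(−1.35) = 0.09. For n = 32 it is 0.12. Even this is generous, because only 19 × 0.02 = 0.4 to 32 × 0.02 = 0.6 unticked users are expected.
- *40% of users stop in one arm, 5% in the other.* d = 0.35. Power is 0.75 (n = 19) to 0.94 (n = 32).
- *20% stop against 5%.* Power is 0.28 to 0.44.

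Pooling the 12 weeks would raise these figures. The measured contrast for a halving of nights would still be about 2 percentage points.

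**Effect on the planned count.** Suppose 30% of an arm use one product and all go from 7 nights to 2. Mean nights per week across the arm fall from 0.30 × 7 = 2.1 to 0.30 × 2 = 0.6, a drop of 1.5/2.1 = 71%. The product count falls from 0.30 to 0.30 × 0.905 = 0.27, about 10%, with independent nights. It does not fall at all if use is exactly 2 nights every week. This is a constructed case, chosen to show the mechanism.

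**The case against.** The strongest reply is that the list does what 5.14.3 asks of it. It repeats weekly from day 1 and records types as well as number, so arms can be compared on any use, on each product, and on starting, stopping and switching. A reader might infer that no change in sleep-aid use could be detected. The documents do not support that, and the stopping scenarios above show that reasonable power is possible. This part of the reply stands.

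It is also true that no document gives the share of users or says whether change would come through fewer nights or through stopping. The size of the loss therefore rests on assumptions.

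A reader might further infer that the primary result is compromised. That does not follow either. Sleep-aid use is exploratory and enters no stated primary or secondary model. A change after randomisation may be a consequence of the intervention, and under the intention-to-treat comparison in 5.1 it does not by itself bias the contrast between arms.

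Nor does listing alcohol spoil the endpoint. The tick reports alcohol taken as a sleep aid, while the drinks item covers all drinking. The two measure different things, and because types are kept, alcohol can be separated at analysis.

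Finally, the survey is known only from the text of app screens, so a follow-up screen that is not reproduced cannot be wholly excluded. No section mentions collecting nights or dose.

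None of this restores the missing information on a continuing product.

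**Conclusion.** The point holds in a limited form. Dose changes in a continuing sleep aid cannot be detected, and changes in nights show only when a whole week is free of use. Under independent nights, a fall from 6 to 3 nights a week moves the chance of a tick from about 1.00 to 0.98, with roughly 9% to 12% power on one week's data if 19 to 32 participants per arm are users. Objective 1.3.3.3 is therefore measured insensitively rather than not at all. The same-dose condition in 1.4.1.5 can be checked only where a product was started or stopped.

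What is affected is an exploratory endpoint and how far it can help interpret the fatigue and sleep results. The sample size and the randomised comparison are untouched. The change is worth making because a stated objective outruns its only instrument, the lost data cannot be recovered later, and the remedy is small.

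**What to change.** 1. In the weekly survey, for anyone who ticks a product, add: *On how many of the past 7 nights did you use any sleep aid?* Those who tick nothing score 0. Ask this once for all products together, because nights per product do not add up: two products on 3 nights each could mean anything from 3 to 6 nights. State in the item whether alcohol counts.
2. For each ticked product, add: *Was your usual dose changed? (no / lower / higher)*, and explain that *usual* means the dose at the start of the study.
3. In 5.14.3, name the comparison: the between-arm difference in change from the day-1 survey in nights per week with any sleep aid, alongside the number and types already planned. Report the alcohol tick separately from the medication count rather than removing it.
4. Separately, reconcile 1.4.1.5 with 1.5.4. One asks participants to agree to keep their dose unchanged; the other places no limit on use. The added items serve whichever rule is kept.

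The cost is two conditional items in an existing in-app survey, a few seconds a week for sleep-aid users only, and a sentence or two in 5.14.3. If enrolment has already begun, change from day 1 will be available only for participants whose first survey carried the new items, and the report should say so.
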